4.3.3 Ethnicity

Ethnicity will be recorded in the eCRF as "Hispanic or Latino"; "Not Hispanic or Latino"; "Not Reported"; or "Un-known".

4.3.4 Race

Race will be recorded in the eCRF as "American Indian or Alaska Native"; "Asian"; "Black or African American"; "Native Hawaiian or Other Pacific Islander"; "White"; or "Other".

4.3.5 Height

Height (in) will be recorded in the eCRF.

4.3.6 Weight

Weight (lb) will be recorded in the eCRF.

4.3.7 Body mass index

Body mass index (BMI; kg/m^2) will be calculated as weight (lb) divided by height squared (in²) and multiplied by 703.

4.3.8 Copy number variant type

Saliva samples will have been processed for identification of genetic mutations; these samples could have been collected during participation in this study or another AEVI-001 study (i.e., the MDGN-NFC1-ADHD-001, MDGN-NFC1-ADHD-101, AEVI-001-ADHD-002 studies). Only those subjects determined to have a copy number variant (CNV) in one of the 8 genes implicated in glutamatergic signaling and neuronal connectivity will be eligible for Part A of this study. The presence of individual CNVs of interest will be determined using a microarray based technology from Illumnia (Illumnia, San Diego) and will be recorded in a separate CNV identification dataset.

An indicator for the CNTN4 CNV will be calculated as:

- IF the subject has at least one CNV type of "CNTN4", THEN set the CNTN4 CNV indicator equal to 1.
- OTHERWISE set the CNTN4 CNV indicator equal to 0.

4.3.9 Kaufman Brief Intelligence Test, Second Edition

The Kaufman Brief Intelligence Test, Second Edition (KBIT-2; Kaufman & Kaufman, 2004) is designed to measure both the verbal and nonverbal intelligence in children and adults (ages 4 years, 0 months through 90 years, 11 months) using a brief, individual format. The KBIT-2 includes 3 subtests; 2 classified as verbal and 1 as nonverbal. Administration of the KBIT-2 yields a Verbal score, Nonverbal score, and intelligence quotient (IQ) Composite score.

The KBIT-2 Verbal, Nonverbal, and IQ Composite standard scores will be recorded in the eCRF.

4.3.10 Child Behavior Checklist

The Child Behavior Checklist (CBCL; Achenbach & Rescorla, 1996) was designed to address the problem of defining child behavior problems. The checklist assesses the behavioral problems and social competencies of children as reported by parents using a standardized format. The CBCL can be self-administered or administered by an interviewer and consists of items related to behavior problems. There are social competency items used to obtain parent reports of the amount and quality of their child's participation in specific tasks and activities. In addition, there are 120 syndrome scale items. Only 118 of these syndrome scale items will be assessed in this study; items 56H and 113 will not be assessed. Each syndrome scale item is scored on a 3-point scale ranging from 0 = "not true (as far as I know)" to 2 = "very true or often true".

Each CBCL competence scale response and syndrome scale item score will be recorded in the eCRF. Various CBCL syndrome scale and problem scores will be calculated as described in Achenbach & Rescorla (1996). For each calculated syndrome scale and problem score, standard scores will also be derived according to the subject's age (6 to 10 years, 11 to 18 years) and sex using normative samples of CBCL scores. All CBCL standard scores are scaled so that a score of 50 is average (with a standard deviation of 10 points) for the subject's respective age and sex categories. Standard scores will be calculated using the Group 2 scoring spreadsheet (i.e., CBCGroup2-ProbScales.xls). Higher scores indicate greater problems.

4.3.10.1 CBCL syndrome scale scores

Eight empirically-based CBCL syndrome scale scores will be calculated as follows:

- Anxious/Depressed syndrome score = sum of items 14, 29, 30, 31, 32, 33, 35, 45, 50, 52, 71, 91, and 112
- Withdrawn/Depressed syndrome score = sum of items 5, 42, 65, 69, 75, 102, 103, and 111
- Somatic Complaints syndrome score = sum of items 47, 49, 51, 54, 56a, 56b, 56c, 56d, 56e, 56f, and 56g
- Social Problems syndrome score = sum of items 11, 12, 25, 27, 34, 36, 38, 48, 62, 64, and 79
- Thought Problems syndrome score = sum of items 9, 18, 40, 46, 58, 59, 60, 66, 70, 76, 83, 84, 85, 92, and 100
- Attention Problems syndrome score = sum of items 1, 4, 8, 10, 13, 17, 41, 61, 78, and 80

- Rule-Breaking Behavior syndrome score = sum of items 2, 26, 28, 39, 43, 63, 67, 72, 73, 81, 82, 90, 96, 99, 101, 105, and 106
- Aggressive Behavior syndrome score = sum of items 3, 16, 19, 20, 21, 22, 23, 37, 57, 68, 86, 87, 88, 89, 94, 95, 97, and 104

Standard scores will be derived for each syndrome scale (as described in Section 4.3.10). In addition, CBCL syndrome scale clinical range categories will be calculated for each syndrome scale as:

- IF the syndrome scale standard score is <65, THEN set the clinical range category equal to "Normal".
- IF the syndrome scale standard score is ≥65 and ≤69, THEN set the clinical range category equal to "Borderline".
- IF the syndrome scale standard score is \geq 70, THEN set the clinical range category equal to "Clinical".

According to the CBCL scoring manual (see Achenbach & Rescorla, 1996, p. 90), these clinical range categories correspond to the following cutoff criteria: scores below the 93rd percentile are considered "Normal", scores between the 93rd to 97th percentile are "Borderline" clinical, and any scores above the 97th percentile are in the "Clinical" range.

4.3.10.2 CBCL problem scores

In addition to syndrome scores, CBCL problem scores will be derived. The Internalizing Problems score will be calculated as the sum of the Anxious/Depressed, Withdrawn/Depressed, and Somatic Complaints syndrome scores; the Externalizing Problems score will be calculated as the sum of the Rule-Breaking and Aggressive Behavior syndrome scores; the Total Problems score will be derived as the sum of all syndrome scale item scores.

Standard scores will be derived for each problem score (as described in Section 4.3.10). In addition, CBCL problem score clinical range categories will be calculated for each problem score as:

- IF the problem standard score is <60, THEN set the clinical range category equal to "Normal".
- IF the problem standard score is ≥ 60 and ≤ 63 , THEN set the clinical range category equal to "Borderline".
- IF the problem standard score is ≥ 64 , THEN set the clinical range category equal to "Clinical".

According to the CBCL scoring manual (see Achenbach & Rescorla, 1996, p. 96), the "Borderline" clinical range category is defined as scores between the 84th to 90th percentiles, inclusive.

4.4 Baseline disease characteristics

4.4.1 Mini International Neuropsychiatric Interview for Children and Adolescents

The date of the Mini International Neuropsychiatric Interview for Children and Adolescents (MINI-KID) assessment and those diagnostic criteria met will be recorded in the eCRF. Only the ADHD subtype (past 6 months) and the medical, organic, drug cause ruled out criteria are required; all other MINI-KID criteria will be recorded only if present. The ADHD (past 6 months) criteria will be recorded as "Combined Presentation", "Predominantly Inattentive Presentation", or "Predominantly Hyperactive Type Presentation". The medical, organic, drug cause ruled out criteria will be recorded as "Yes", "No", or "Uncertain".

4.4.2 Age at ADHD diagnosis/Time since ADHD diagnosis

Date of ADHD diagnosis will be recorded in the eCRF. Age at ADHD diagnosis will be calculated in years as the date of ADHD diagnosis minus the date of birth. Time since ADHD diagnosis will be calculated in years as the date of consent minus the date of ADHD diagnosis.

4.4.3 Age at ADHD Onset

Age at ADHD Onset in years will be recorded in the eCRF.

4.5 **Prior and concomitant medications**

For each prior or concomitant medication, the medication name, indication, dose, frequency, route, start date, ongoing indicator, and stop date (for those medications not ongoing) will be recorded in the eCRF. Each medication will be coded using the World Health Organization Drug Dictionary (WHODrug) Enhanced version September 2016.

All medications will be classified according to the study period in which its use occurred (i.e., Prior, Concomitant, or Post-treatment). Prior medications are those that started and ended before the initiation of study drug. Concomitant medications are (i) those that started before initiation of study drug and continued after initiation of study drug or (ii) those that started after the initiation of study drug; any medications that started on the same day as the initiation of study drug will be considered concomitant. Post-treatment medications are those that started after completion of study drug.

If the start date (or end date) of a medication is completely unknown (i.e., the day, month, and year are all missing) or only the day is known, then the start date (or end date) will not be imputed. Unless the end date is before the start date of study drug, the medication will be considered concomitant.

For a partial start date of medication, the following conventions will be used for imputing the start date:

- If the year is present and the month and day are missing, then the month and day will be set to January 1.
- If the year and day are present and the month is missing, then the month will be set to January.
- If the year and month are present and the day is missing, then the day will be set to the first day of the month.
- If the imputed start date of medication is after the non-imputed end date of medication, then the start date will be set to the end date of medication.

For a partial end date of medication, the following conventions will be used for imputing the end date:

- If the year is present and the month and day are missing, then the month and day will be set to December 31.
- If the year and day are present and the month is missing, then the month will be set to December.
- If the year and month are present and the day is missing, then the day will be set to the last day of the month.

4.6 Study drug exposure variables

Drug accountability will be performed at each visit during the treatment period. At each visit that study drug is dispensed to subjects, the dose level, investigator dose assessment, quantity dispensed, intended first dose date, and intended first dose AM/PM will be recorded in the IRT system. At each visit that study drug is returned, the quantity remaining, intended last dose date, intended last dose AM/PM, percent compliance, and an overdose flag will be recorded in the IRT system. The percent compliance for the prior dosing period will be derived as the number of capsules taken divided by the expected number of capsules taken. For percent compliance calculations, capsules not returned will be assumed taken.

- Dose level will be recorded as "Level 1 (100mg or placebo bid)", "Level 2 (200mg or placebo bid)", or "Level 3 (400mg or placebo bid)".
- Intended first and last dose AM/PM values will be recorded as "AM Only", "PM Only", or "AM and PM".
- Investigator dose assessment will be recorded as "Increase the dose", "Maintain the Dose", or "Decrease the dose".
- Overdose flag will be recorded as "Yes" or "No".

Prior to analysis, all study drug exposure data recorded or derived in the IRT system will be transferred into the eCRF.

Optimized dose will be calculated as the dose level dispensed at Week 4 (Visit 6). Total study drug exposure (in mg) will be calculated as the sum of all administered doses not returned. Duration of total exposure (in days) is calculated as date of last dose - date of first dose + 1.

Overall percent compliance for the entire treatment period will also be derived. To calculate overall percent compliance, a weight for each weekly percent compliance is required; this weight value will be calculated as the number of doses expected during that week divided by the total number of doses expected during the subject's participation in the study. The total number of doses expected will be calculated as:

- IF the latest intended last dose AM/PM value is "AM Only", THEN the total number of doses expected is equal to (the latest intended last dose date the earliest intended first dose date + 0.5) \times 2
- IF the latest intended last dose AM/PM value is "AM and PM", THEN the total number of doses expected is equal to (the latest intended last dose date the earliest intended first dose date + 1) \times 2

Overall percent compliance will be calculated as:

$$\sum_{i=1}^{6} (\text{Percent Compliance})_i \times (\text{Weight})_i, \text{ where } i \text{ is the study week of dosing.}$$

In addition, overall compliance categories will be calculated as:

- <80%
- \geq 80% and \leq 120%
- >120%

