### 9.7 Dose Adjustment Criteria

The duration of the dose-optimization phase is 4 weeks to allow for weekly titration up to the highest dose and 1 titration down to the previous dose, if necessary.

Following enrollment, all subjects will begin taking AEVI-001 or placebo and will be evaluated after approximately 7 days ( $\pm$  2 days) for safety and efficacy. Subjects may be titrated weekly to the next available dose strength after approximately 7 days ( $\pm$  2 days) on the previous dose, based on the overall response of the subject. Additionally, if needed, a subject may be down-titrated once to the previous dose level to optimize tolerability and efficacy. Subjects unable to tolerate the lowest available dose (100 mg twice daily or placebo) will be discontinued from the study. Subject response will be categorized by the investigator as 1 of 3 conditions and associated actions, with titration continuing until an "acceptable response" is achieved:

□ Intolerable response (i.e., intolerable side effects): Requires the subject to be tapered to a lower dose of AEVI-001 or placebo (if available). However, if this lower dose produces an intolerable response as well, the subject should be discontinued from the study.
 □ Ineffective response: Subject has not achieved a CGI-I score of <3. This response requires increasing titration of AEVI-001 or placebo to the next available dose strength, provided tolerability is acceptable, followed by weekly evaluation.

 □ Acceptable response: A response is defined as acceptable if it shows a significant reduction in symptoms, defined by a CGI-I score of <3, with tolerable side effects. Subjects categorized as "acceptable" may be maintained at their current dose of AEVI-001 or placebo for the remainder of the study. Subjects who are tolerating IP at the highest

available dose but do not achieve an acceptable response should be continued in the study.

If, in the opinion of the investigator, the "acceptable" dose is well tolerated and the subject would potentially receive additional symptom reduction, the dose may be increased to the next dosage strength.

If, in the opinion of the investigator, the subject experiences unacceptable tolerability, the dose of AEVI-001 or placebo may be reduced (if available) by 1 dose level (to the previous dose). If the subject tolerates the dose reduction and maintains symptom control, the subject may be maintained at that reduced dose for the remainder of the study.

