Only 1 dose reduction is permitted during the dose optimization phase of the study. Once a dose has been reduced no further changes to the dose will be allowed. Visit 5 will be the last visit at which titration (increase or reduction) can occur. Once a subject has reached an optimal dose, this dose should be maintained during the remainder of the dose optimization phase and will be the dose received during the dose maintenance phase (2 weeks). Subjects who are unable to tolerate AEVI-001 or placebo will be discontinued. A 7-day (+2 days) follow-up call will occur after the last dose of IP.

Subjects who discontinue because they are unable to tolerate the IP must complete all early termination (ET) visit assessments required during the last study visit. These subjects will also receive a 7-day follow-up call after discontinuing study treatment.

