### 14.3.3 Exposure and Compliance

Exposure to IP will be summarized for all participating subjects. Subjects will be described with respect to cumulative exposure as well as categorized by the highest dose received. Compliance with study medication will be determined for each subject overall and by visit. Based on capsule counts, the number of doses administered will be expressed as the proportion of doses scheduled by week and overall. Doses not returned will be assumed taken for the purposes of calculating compliance. Additionally, compliance will be calculated within IWRS. A subject will be considered non-compliant if their overall compliance is less than 80% or greater than 120%. This assessment will be completed at the end of the study.

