5.5 Safety analyses

For all safety endpoints, descriptive statistics will be presented by treatment group and visit (where applicable) using the safety analysis set. In addition, some safety endpoints may be further summarized by optimized dose (see Section 4.6). In summaries of change from baseline safety variables, only subjects with both baseline and post baseline data will be included. No formal hypothesis tests will be performed for any safety endpoint.

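### In any safety table by optimized dose, 400 mg events that forced a reduction or withdrawal before Visit 6 cannot appear under 400 mg

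*SAP*

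**What the plan says.** SAP 4.6 gives each subject one dose label: "Optimized dose will be calculated as the dose level dispensed at Week 4 (Visit 6". SAP 5.5 sets the main presentation, in which "descriptive statistics will be presented by treatment group and visit (where applicable) using the safety analysis set". It then allows that "some safety endpoints may be further summarized by optimized dose". The adverse event tables in SAP 5.5.2 are all by treatment group, and no variable for dose at event onset is defined.

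Protocol 9.7 decides who holds which label. An intolerable response "Requires the subject to be tapered to a lower dose of AEVI-001 or placebo (if available"; "if this lower dose produces an intolerable response as well, the subject should be discontinued from the study". Further, "Once a dose has been reduced no further changes to the dose will be allowed", and "Visit 5 will be the last visit at which titration (increase or reduction) can occur".

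For exposure, Protocol 14.3.3 has subjects "categorized by the highest dose received". SAP 5.5.1.2 summarises optimized dose, total exposure and duration, but not highest dose. SAP 6.1 declares no change from the protocol.

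**The concern.** The Visit 6 dose is reached by titrating on tolerability, so grouping adverse events by it conditions on an outcome of those same events. Three things follow:

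- An event that causes a reduction is tabulated under a level at which it did not occur.
- A subject who leaves before Visit 6 has no level at all.
- Events from the early low-dose weeks are credited to whatever level the subject ended on.

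A reader who takes such a table as dose-specific tolerability, above all at the top dose, would be misled on the events that matter most for choosing a dose.

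**Working it through.** **1. Tracing the label.** There is no stated figure to reproduce; the check applies the titration rules to the definition. Everyone starts at 100 mg, steps are weekly, and Visit 5 is the last titration visit. At scheduled visits 400 mg is therefore first dispensed at Visit 4 (start of week 3) or Visit 5 (start of week 4).

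- Intolerable event at 400 mg in week 3: reduced at Visit 5 and locked, so the label is a lower level.
- Intolerable event at 400 mg in week 4: if the subject stops, nothing is dispensed at Visit 6 and there is no label. The schedule of events also lists an investigator dose assessment at Visit 6, which does not fit a last titration at Visit 5; those sections must be reconciled. If a reduction did occur at Visit 6, the label would be the lower level. Neither route leads to a 400 mg label.
- Intolerable event in weeks 5 to 6: the label is already fixed at 400 mg, so the event stays there.

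**2. Size for intolerable events.** The inputs are assumed, because the documents give none. Weekly TEAE chance at 100/200/400 mg is 10/10/10%, 5/10/20% or 5/10/30%. The intolerable share is 20%, 30% or 10/20/50% respectively. The chance of up-titration when tolerated is 60%, 80% or 95%. That makes nine scenarios, simulated with 60,000 subjects each; an intolerable event from week 4 on is taken to end treatment.

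Let p be the weekly chance of an intolerable event at 400 mg. By Visit 6 label only weeks 5 and 6 count: 1 − (1 − p)². By onset, a subject has 3 or 4 weeks at 400 mg: 1 − (1 − p)³ to 1 − (1 − p)⁴.

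| p | By label, formula | By label, simulated | By onset, formula | By onset, simulated |
|---|---|---|---|---|
| 10% × 20% = 2% | 4.0% | 3.9–4.1% | 5.9–7.8% | 6.9–7.7% |
| 20% × 30% = 6% | 11.6% | 11.3–11.8% | 16.9–21.9% | 19.4–21.7% |
| 30% × 50% = 15% | 27.8% | 27.5–28.1% | 38.6–47.8% | 44.2–46.9% |

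Among subjects labelled 400 mg, intolerable events in weeks 1 to 4 were exactly 0 in all nine scenarios. Of intolerable events that began at 400 mg, 43–55% appeared under 400 mg, 17–28% under a lower level and 26–31% under no level. Between 4% and 14% of subjects had no Visit 6 dose.

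**3. Overall TEAE incidence.** Take the flat case, with no true dose effect. A 400 mg label requires no intolerable event in weeks 1 to 4. The chance of no TEAE in such a week is 0.90/0.98, so incidence is 1 − (0.90/0.98)⁴ × 0.90² = 1 − 0.7113 × 0.81 = 42.4% (simulated 42.3–42.5%). The simulated label figures at lower levels are 44–85% at 200 mg and 58–100% at 100 mg, a false inverse dose relation.

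The bias at 400 mg does not always run one way. By onset the flat case gives 31.4–33.6% at 400 mg, below the label figure, because 33–38% of the TEAEs shown under 400 mg in that case began at 100 or 200 mg. In the steepest case the label gives 69.2–70.4% and onset 71.7–75.2%.

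**4. Why onset needs a time denominator.** In the flat case with 60% up-titration, incidence by onset is 16.9%, 19.0% and 31.4% at 100, 200 and 400 mg, although the weekly chance is 10% at every level. That gradient reflects time spent at each level, not dose.

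**The case against.** The strongest reply is that the SAP does not commit to this table. The wording is permissive, covers some endpoints only, and is additional to treatment-group tables on the full safety set. Those tables lose no dosed subject, and withdrawals due to TEAEs have their own table and listing. The safety objective is AEVI-001 against placebo, not dose against dose. With about 21 active subjects (42/2) over three levels, any by-dose table is descriptive, and dose at onset can be recovered from the listings. All of this stands and limits the point to the optional table.

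Four stronger readings are tempting and not supported:

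- A reader might infer that 400 mg will look tolerable by construction on every safety measure. That holds only for dose-limiting events before Visit 6. Low-dose events carried into the 400 mg column can raise its overall incidence, and intolerable events in weeks 5 to 6 remain there.
- A reader might infer that the SAP excludes early discontinuers. It does not say so. It gives no rule for them, and SAP 5 leaves missing categories out of percentages.
- A reader might infer that the protocol requires safety tables by highest dose received. Protocol 14.3.3 uses that category for exposure; the protocol's safety sections name no dose grouping.
- A reader might treat highest dose as the cure. It too assigns low-dose events to 400 mg and depends on tolerability.

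It is also fair that dose at onset is imperfect: dose is not randomised, and everyone's first week is at 100 mg.

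**Conclusion.** The point holds for any safety summary by optimized dose, the only by-dose safety grouping the SAP names. If Protocol 9.7 is followed, dose-limiting 400 mg events from before Visit 6 shown under 400 mg number zero, whatever their true frequency. This follows from the rules and needs no assumed figure. The size of the resulting understatement (4–28% against 7–47% for intolerable events at 400 mg) rests on the assumed weekly chances and is an illustration, not a forecast. Overall TEAE incidence at 400 mg may be too high or too low. The treatment-group safety analysis stands.

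Separately, the omission of highest dose from the exposure summaries, with no change declared, is a small discrepancy between protocol and SAP whether or not a by-dose safety table is produced.

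**What to change.** - In SAP 5.5, for any by-dose adverse event summary, use the dose level being taken at event onset, with subject-days at each level as denominator. State that dose is not randomised and is confounded with time on study.
- In any table by optimized dose, show subjects without a Visit 6 dose as their own column.
- In SAP 5.5.1.2, restore highest dose received as an exposure category, or declare its removal in SAP 6.1.
- Keep optimized dose as an exposure descriptor.

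The cost is SAP wording, one derived variable and one table. The IRT already records dose level and intended first dose date at each dispensing (SAP 4.6), and the AE start date is in the eCRF (SAP 4.8.1). Because SAP 4.8.1 sets a wholly missing start date to the first dose date, such events would fall under 100 mg by default and should be flagged. A small downside is that one subject can appear in more than one dose column.
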